#### **4.2.6. Secondary Outcomes**

Secondary measures of lung function will be comparison of resistance data at available frequencies including r7, r13, and r19; reactance at other available frequencies including 13 and 19 Hz, impedance data including resistance as a function of frequency  $R(f)$ , reactance as a function of frequency  $X(f)$ , and coherence at each frequency  $Coh(f)$ ; resonance frequency ( $f_{res}$ ); reactance area  $AX7$ ; reactance difference  $\Delta X7$ ; tidal volume and respiratory rate. In addition measures over time will allow us to create normative data curves of changes in these measurements over time in the given populations.

#### **4.2.7. Compliance Monitoring**

All participants are hospitalized in the UAB RNICU or newborn nursery, so clinical history including medication adherence will be recorded.

Oscillometry will be administered by physicians and nurses trained in the care of newborn infants and in the use of the forced oscillation technique device. Measurements will be repeated until a stable consistent measurement is obtained as recommended by the manufacturer of the device. The coefficient of variation between three valid measurements with the device should not exceed 15%.

### **4.3. POTENTIAL RISKS AND BENEFITS TO SUBJECTS**

Infants enrolled in this study are not expected to have risks above routine care. Measurements are taken by placing a new disposable mask over the baby's mouth and nose and allowing them to breathe normally. It is possible that some infants will find having a mask on their face for 5-10 seconds uncomfortable but this is immediately reversible by removal of the mask.

## SECTION 5. ANALYTICAL PLAN

---

### 5.1. STATISTICAL ANALYSIS PLAN

Results will be analyzed by the Student's t test, as appropriate for parametric data, and by Mann-Whitney U rank sum test for nonparametric data. A  $p$  value of  $<0.05$  will be considered statistically significant.

Non-independent parametric data will be analyzed by the paired Student's t test, and Wilcoxon signed rank test for non-independent non-parametric data.

Chi-square or Fisher's exact test will be used as appropriate to analyze categorical data.

Analysis of covariance and multiple regression models will be used to examine the interaction between, and the independent effects of factors including birth weight, gestational age, gender, ethnicity, socioeconomic group, maternal smoking, type and severity of lung disease, treatment with surfactant (including number of doses), days of mechanical ventilation before study entry, days of respiratory support before study entry, treatment with antenatal steroids, and treatment with postnatal steroids upon primary and secondary outcomes.

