### **4.1. STUDY POPULATION**

This study will investigate lung function in term ( $\geq 37$  weeks) and preterm (22-36 weeks) infants with and without newborn lung diseases (BPD, RDS, TTN, MAS).

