#### **4.1.2. Exclusion Criteria**

Infants will be excluded from this study if they have any of the following:

A major congenital malformation (e.g., cardiac disease or diaphragmatic hernia).

A neuromuscular condition that affects respiration (e.g., spinal muscular atrophy or myopathy).

A terminal illness or decision to withhold or limit support (e.g., chromosomal abnormality or neoplasm)

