#### **4.2.4. Control or Monitoring of Co-interventions**

Aim 1 control: baseline oscillometry measurements will be compared over time between preterm infants and term infants without lung disease as defined by need for respiratory support.

Aim 2 control: preterm infants with RDS who go on to develop BPD will be compared with preterm infants with RDS who do not go on to develop BPD. Preterm infants who do not develop BPD will serve as controls for RDS infants who develop BPD.

Aim 3 control: baseline pulmonary function tests and serial changes over time will be compared between infants with and without lung disease. Preterm infants without lung disease will act as controls for preterm infants with lung disease. Term infants without lung disease will act as controls for term infants with lung disease.

Aim 4 control: The timing of pulmonary function testing among infants with lung disease will be recorded in relation to the timing of interventions, as ordered by the treating physician, which may affect pulmonary function including bronchodilators, steroids, diuretics, methylxanthines, different forms of physical therapy, and nebulized/inhaled medications, to determine the effects of these treatments on pulmonary function pairing the pre-treatment pulmonary function values (control) for an individual patient with the post-treatment values (intervention) for the same individual patient.

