### 5.2. SAMPLE SIZE

This observational study will include all eligible infants enrolled at UAB RNICU and NBN.

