#### **Aim 1 (Comparison of lung compliance in term and pre-term infants)**

Assuming lung reactance at 7 Hz ( $X_7$ ) initial measurements will have an absolute 20% difference (more negative) in preterm infants without RDS compared to term controls will need to recruit 264 infants (132 term and 132 preterm infants) assuming power of 90%, type I error rate of 5% and standard deviation of 0.5 of the mean.

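### Infants from the same birth may all enrol, but the between-group tests and regressions treat every infant as independent, and the 90% power does too

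*Combined protocol and SAP*

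**What the plan says.** **Who enters.** Section 5.2 opens: "This observational study will include all eligible infants enrolled at UAB RNICU and NBN". Section 4.1.1 asks for a minimum gestation, parental consent, admission to one of the two units and a period off ventilator/CPAP support. The list in Section 4.1.2, introduced by "Infants will be excluded from this study if they have any of the following", covers major malformation, neuromuscular disease, and terminal illness or limited support. Neither list excludes multiples or restricts a family to one infant. Twins, multiples, siblings and clustering by mother are not mentioned anywhere in the document.

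**How groups are compared.** Section 5.1 says: "Results will be analyzed by the Student's t test, as appropriate for parametric data, and by Mann-Whitney U rank sum test for nonparametric data". Categorical data go to chi-square or Fisher's exact test. The adjusted analyses are described as: "Analysis of covariance and multiple regression models will be used to examine the interaction between, and the independent effects of factors including birth weight", followed by a list of further factors. Mother, family and birth set are not on that list.

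**What is said about dependence.** One sentence: "Non-independent parametric data will be analyzed by the paired Student's t test, and Wilcoxon signed rank test for non-independent non-parametric data". The pairing the plan describes is in Section 4.2.4, Aim 4: "pairing the pre-treatment pulmonary function values (control) for an individual patient with the post-treatment values (intervention) for the same individual patient".

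**Sample size.** For Aim 1, X7 "will have an absolute 20% difference (more negative) in preterm infants without RDS compared to term controls", with an SD of 0.5 of the mean, 90% power and a 5% type I error, giving 132 per group. Aim 2 and the RDS, BPD and TTN parts of Aim 3 use the same 132 per group. No design effect is mentioned.

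**The concern.** Co-twins share gestational age, mother, antenatal exposures and much of their genetic make-up. Section 5.1 itself lists gestational age, antenatal steroids, maternal smoking, ethnicity and socioeconomic group as factors whose effect on the outcomes is to be examined. If those factors matter, the X7 values of siblings will be correlated.

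An independent-sample test then uses the wrong standard error. If siblings sit in the same comparison group, each sibling adds less information than the test credits, the standard error is too small and p values are too optimistic. If siblings are split between the two groups, their shared component cancels in the difference, the standard error is too large and the test is conservative. At stake are the accuracy of the 5% level in Aims 1-3 and the 90% power, which counts every infant as a separate unit.

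**Working it through.** **1. The plan's own figure.** Inputs from Section 5.2, Aim 1: difference 0.20 of the mean, SD 0.50 of the mean, alpha 5% (taken as two-sided), power 90%.

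n per group = 2 × (1.960 + 1.282)² × 0.50² / 0.20² = 131.3, rounded up to 132. This matches the stated figure. With 132 per group the standard error is 0.5 × √(2/132) = 0.0615 and power is Φ(0.2/0.0615 − 1.960) = 90.1%. So the stated power requires 264 independent infants.

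**2. Assumed inputs (not in the documents).**
- f, the share of a preterm group's infants who are in twin pairs with both members in that group: 10-30%.
- ρ, the within-pair correlation of X7: 0.3-0.7.
- Term groups: design effect taken as 1.

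**3. Formulas.**
- Design effect in a group: DE = 1 + fρ. Low: 1 + 0.10 × 0.3 = 1.03. High: 1 + 0.30 × 0.7 = 1.21.
- D = mean of the two groups' DE.
- True size of the nominal 5% test: 2 × [1 − Φ(1.960/√D)].
- Power of a valid 5% test at 132 per group: Φ(0.2/SE − 1.960), with SE = 0.5 × √((DE₁ + DE₂)/132).

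**4. Results when co-twins are in the same group.**

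| Comparison | DE₁, DE₂ | D | True size | SE | Power |
|---|---|---|---|---|---|
| Aim 1, low | 1.03, 1 | 1.015 | 5.2% | 0.0620 | 89.7% |
| Aim 1, high | 1.21, 1 | 1.105 | 6.2% | 0.0647 | 87.1% |
| Both preterm, low | 1.03, 1.03 | 1.03 | 5.3% | 0.0625 | 89.3% |
| Both preterm, high | 1.21, 1.21 | 1.21 | 7.5% | 0.0677 | 84.0% |

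The last two rows apply to Aim 2 and to the RDS and BPD parts of Aim 3, with 132 in each group.

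**5. Results when co-twins are split.** If every pair has one member in each group, the variance factor for the difference becomes 1 − fρ. Over the same ranges that is 0.97 down to 0.79, and the true size is 4.7% down to 2.7%. A simulation of the two-sample t test (20,000 replicates, 132 per group, f = 20-30%, ρ = 0.3-0.8) gave 2.5-4.1% with all pairs split and about 5% with half of them split. The sign of the error therefore depends on the mix of concordant and split pairs.

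**6. Can the paired-test sentence cover this?** A paired test needs one member of each pair on each side of the comparison. It has no place for singletons, and none for two co-twins in the same group. The latter is the expected case in Aim 1, because co-twins usually have the same gestational age.

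**The case against.** The strongest reply is that the effect is small, assumed, and partly dealt with.

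- **No figures in the documents.** A reader might infer that multiples are known to be common in this cohort and that the p values are therefore wrong by a known amount. The documents give no share of multiples and no correlation, so neither statement can be made. This stands. Each infant must also be consented and meet the respiratory-support criterion, so siblings may enrol but need not both do so.
- **Direction.** A reader might infer that significance is always overstated. That is likely in Aim 1, but not established for Aim 2 or the preterm parts of Aim 3, where pairs can be split. This stands.
- **Reach.** The preterm assumptions do not extend to the TTN and MAS comparisons, which are term against term, and they apply to only one group in Aim 1. This stands, and is why Aim 1 has its own range.
- **Covariates.** Adjusting for gestational age, antenatal steroids, maternal smoking, ethnicity and socioeconomic group would absorb part of the sibling correlation. True for the regression models, though not necessarily all of it. It does nothing for the unadjusted tests, which are the ones the sample sizes correspond to.
- **Power.** In Aim 2, enrolment of infants with RDS continues until the BPD target is met, so the non-BPD group may exceed 132. As an illustration, 132 against an assumed 203 at a design effect of 1.21 gives SE = 0.5 × √(1.21 × (1/132 + 1/203)) = 0.0615 and power of about 90%. The power loss in Aim 2 may therefore be smaller than the table shows. Larger numbers do not correct the size of the test.

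What the reply does not answer is the omission itself: siblings are eligible, and no planned between-group method allows for them.

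**Conclusion.** The point holds as a modest defect in the analysis plan. Followed as written, Section 5.1 gives incorrect between-group standard errors wherever siblings are enrolled. Under the assumptions stated, and with co-twins in the same group, a nominal 5% test runs at about 5.2-6.2% in Aim 1 and about 5.3-7.5% where both groups are preterm. Power is about 90-87% and 89-84% respectively, against the stated 90%. Where co-twins are split, the test is conservative instead, so for Aim 2 and the RDS and BPD parts of Aim 3 the net direction is unknown.

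A reader might go further and conclude that the study's comparisons are invalid or the sample size miscalculated. The documents do not support that. The 132 per group is correct for independent infants, and even the upper end of the assumed range moves size and power by a few percentage points. The case for acting is that the size and sign of the error depend on a mix of sibling pairs that the plan neither describes nor models, and that the remedy is cheap.

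**What to change.** 1. Record a mother or birth-set identifier for every enrolled infant.
2. In Section 5.1, specify that the Aim 1-3 between-group comparisons of X7 use linear models with standard errors clustered by mother, or with a random intercept for mother, in place of the independent-sample t tests. Either form keeps every infant and is valid whether co-twins share a group or are split.
3. In Section 5.2, state that the 90% power assumes independent infants. The range above can be given as a sensitivity statement.

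Cost: one data item, a line or two of text, slightly more analysis work and a slightly less favourable power figure. No clinical procedure changes. If no multiples enrol, the result will be close to the Student t test but not always identical: with singletons only, clustered standard errors become heteroscedasticity-robust ones, which differ from the pooled standard error when group sizes and variances are unequal.

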### **3.2. SECONDARY HYPOTHESIS OR QUESTIONS (S) (IF APPLICABLE)**

- 1) Oscillometry can detect disease progression (e.g., BPD, RDS, TTN and MAS) and resolution in infants hospitalized in the UAB NICU.
- 2) Oscillometry can inform therapeutic response to common pulmonary interventions (e.g., systemic steroids, inhaled steroids, and diuretics) in infants hospitalized in the UAB NICU.
- 3) To determine how pulmonary function differs over time between preterm infants with RDS which resolves and preterm infants with RDS who go on to develop BPD.
- 4) To determine the effects on pulmonary function measurements of medications and treatments given to newborn infants to treat bronchopulmonary dysplasia including physical therapy, methylxanthines, furosemide, chlorothiazide, inhaled and systemic corticosteroids, cromolyn sodium, and albuterol.

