#### **4.2.3. Study Intervention and Comparison**

Term and preterm infants with and without newborn lung disease will have serial oscillometry to evaluate neonatal lung function. Infants will have pulmonary function testing performed using the forced oscillation technique at baseline after enrollment in the study. This will be repeated after 24 hours, 48 hours and once per week thereafter among infants who remain hospitalized.

Infants with lung disease who are receiving pulmonary medications or treatments for lung disease, as per physician order, will have additional measurements of pulmonary function before and after these treatments are given.

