#### **4.2.5. Primary Outcome**

The primary outcome will be change in lung reactance at 7 Hz ( $X_7$ ) quantified by oscillometry in each comparison group.

In Aim 1, we will compare lung function between term and preterm infants without lung disease at baseline, 24 hours, 48 hours, 72 hours, 7 days, and weekly thereafter until discharge.

In Aim 2, we will compare lung function between preterm infants with RDS who develop BPD and those who do not develop BPD.

In Aim 3, we will longitudinally evaluate change in lung function in NICU patients with lung disease (BPD, RDS, TTN, MAS) at diagnosis, 24 hours, 48 hours, 72 hours, 7 days, and weekly thereafter until resolution of disease state or NICU discharge.

In Aim 4, we will longitudinally evaluate lung function response to therapeutic intervention.

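### Change in X7 is the primary outcome but Section 5.2 powers the initial value; Section 5.1 ranks neither and has no repeated-measures model, and Aim 4's paired test would credit background change to treatment

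*Combined protocol and SAP*

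**What the plan says.** **Outcome and visits.** Section 4.2.5: "The primary outcome will be change in lung reactance at 7 Hz", with no interval or reference visit. Aim 1 is compared "at baseline, 24 hours, 48 hours, 72 hours, 7 days, and weekly thereafter until discharge"; Aim 3 follows the same times from diagnosis. No visit is ranked. Section 4.2.3 gives a slightly different schedule, without the 72-hour test: "repeated after 24 hours, 48 hours and once per week thereafter among infants who remain hospitalized".

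**Comparisons over time.** Section 4.2.4, Aim 3: "baseline pulmonary function tests and serial changes over time will be compared between infants with and without lung disease". Section 3.2, item 3: "To determine how pulmonary function differs over time between preterm infants with RDS which resolves" and those who develop BPD, which is the Aim 2 contrast.

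**Sample size.** Section 5.2 bases Aims 1 to 3 on initial measurements.

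**Analysis.** Section 5.1 names the t test and Mann-Whitney test for independent data. For repeated data it says "Non-independent parametric data will be analyzed by the paired" t test, or the Wilcoxon signed rank test. It adds analysis of covariance and multiple regression with a list of covariates.

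**Aim 4.** Section 4.2.3: treated infants "will have additional measurements of pulmonary function before and after these treatments are given". Section 4.2.4 records test timing relative to treatment and states the purpose as "to determine the effects of these treatments on pulmonary function pairing the pre-treatment pulmonary function values (control) for an individual patient" with that infant's later value. The Abstract describes the Aim 4 treatments as chronic.

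**The concern.** There are two linked gaps.

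**Serial X7 (Aims 1 and 3, and the RDS with versus without BPD comparison).** An initial value and a change are different quantities, with different variances and different power. Section 5.2 uses one, Section 4.2.5 names the other, and Section 5.1 chooses neither. A paired test takes two values per infant, so it can neither use five or more visits nor compare trajectories between groups. The regression models could, but only with an age or visit term and an allowance for repeated values in the same infant, and neither is specified. If the visit or summary is chosen after the data are seen, a difference at one of several visits may be chance. Later visits also contain only infants still in hospital, so they over-represent sicker infants, and separate tests at each visit do nothing about that.

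**Aim 4.** A one-group before/after test measures total change. Maturation, disease course and regression to the mean all enter the estimate, yet Section 4.2.4 would report the result as a treatment effect. For physical therapy and cromolyn, which Section 5.2 frames as non-inferiority with a 15% margin, favourable drift can produce false non-inferiority and adverse drift can hide true non-inferiority.

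**Working it through.** **Inputs from Section 5.2:** SD 0.5 of the mean; two-sided 5% (sidedness is not stated; a one-sided test gives 108 per group and does not reproduce 132); differences of 0.20 (Aims 1 and 2 and most of Aim 3), 0.50 (MAS), and 0.15, 0.20 or 0.30 (Aim 4). **Assumed, because the documents give no figure:** within-infant correlation ρ and background drift.

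**1. The plan's figures.**
- Two groups, n = 2[0.5(1.960 + 1.282)/0.20]² = 131.3, so 132 per group. This matches, for a single initial measurement. MAS: 21.01, against 21 stated.
- Aim 4 as one group of pairs with SD of change 0.5, n = [0.5(1.960 + 1.282)/δ]²: 116.7, 65.7 and 29.2 for δ = 0.15, 0.20 and 0.30, against 120, 70 and 30 stated. Noncentral-t power at the stated totals is 90.3%, 91.0% and 88.8%. So these totals fit a one-group paired test; no comparator is powered.
- Exceptions: cromolyn is stated at 80% power, which needs about 88 pairs rather than 120. Three therapies say 60 per arm: 60 pairs give 62.8% power for 0.15, and two separate groups would need 234 per arm at 90% (175 at 80%).

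**2. Power if a change score is primary.** SD of change = 0.5√[2(1 − ρ)]; 132 per group, difference in change 0.20:

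| ρ | SD of change | Power |
|---|---|---|
| 0 | 0.707 | 63% |
| 0.3 | 0.592 | 78% |
| 0.5 | 0.500 | 90% |
| 0.7 | 0.387 | 99% |

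**3. Visit-by-visit testing.** Chance of at least one false positive in five equicorrelated tests at 0.05 (baseline, 24, 48 and 72 hours, 7 days). For ρ = 0 it is 1 − 0.95⁵ = 22.6%. For ρ = 0.3, 0.5, 0.7 and 0.9 it is about 21%, 18%, 15% and 10%.

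**4. Aim 4 with no treatment effect.** Two-sided paired t test, noncentrality = drift × √n / 0.5. For example, n = 120 and drift 0.10 give 0.10 × 10.95/0.5 = 2.19. Proportion significant:

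| Drift (share of mean) | n = 120 | n = 70 | n = 30 |
|---|---|---|---|
| 1% | 5.5% | 5.3% | 5.1% |
| 5% | 19% | 13% | 8% |
| 10% | 58% | 38% | 19% |

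Regression to the mean alone could be of this order. If infants were treated only when in the worse half of X7, the expected untreated change is (1 − ρ) × 0.5 × 0.798, or 0.20 at ρ = 0.5 and 0.04 at ρ = 0.9.

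**5. Non-inferiority at n = 120, one-sided 2.5%, margin 0.15.** With a true 15% loss, favourable drift of 5% or 10% gives false non-inferiority in 19% or 58%. With no true change, adverse drift of the same size cuts power from 90% to 58% or 19%.

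**6. Cost of a comparator in Aim 4.** Comparing change between equal groups of 120, 70 or 30 gives about 64%, 65% or 63% power for 0.15, 0.20 or 0.30. This is a rough guide, not the power of a mixed model.

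**The case against.** Several stronger readings are tempting, and the documents do not support them.

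- *The plan has no time point at all.* Section 5.2 points to the initial measurement for Aims 1 to 3, and 132 per group reproduces for exactly that test, which is valid. The defect is that this conflicts with a change outcome and is not carried into Section 5.1.
- *The plan will test every visit at 0.05.* Nothing says so. One change score per infant would also be valid and would keep 5% error. The 10% to 23% is conditional, and its top end needs zero correlation between tests of the same infants. Taking 0.5 as the SD of both a single value and a change implies ρ = 0.5, or about 18%.
- *Section 5.1 offers only t tests.* It also names analysis of covariance and regression, and covariance analysis could adjust one follow-up value for baseline. That is a partial answer: it does not handle many visits per infant.
- *Aim 4 findings will be false.* The drift values have no source in the documents. For tests around a single administration, drift of about 1% leaves the error near 5%. Section 4.2.4 already records timing; what is missing is a prespecified interval.

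It can fairly be said that the absence of a comparator is a design limit of an observational study. That stands, and it is why the main Aim 4 remedy is wording. What the objections leave intact is the unresolved primary contrast, the lack of a method for serial data, and a stated Aim 4 inference that the design cannot carry.

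**Conclusion.** The point holds in limited form. The primary outcome and the powered quantity disagree, Section 5.1 does not choose between them, and none of its methods as specified suits five or more values per infant. The initial-measurement t test is sound and adequately sized; the gap concerns the serial and treatment claims. The possible size is a family-wise error of roughly 10% to 23% under visit-by-visit testing, and in Aim 4 a false-positive rate of 19% or 58% at n = 120, 13% or 38% at n = 70, and 8% or 19% at n = 30 for drift of 5% or 10%. These rest on assumed correlation and drift and on an SD of change of 0.5. The Aim 4 concern is small for short pre/post intervals and larger for treatments assessed over days or weeks. It should be fixed before the data are examined.

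**What to change.** 1. **Reconcile Section 4.2.5 with Section 5.2** by naming one primary contrast per comparison in Section 5.1. The initial-measurement t test is the one that 132 per group supports; serial X7 is then secondary. If a change score is preferred, name its interval (48 hours appears in both visit schedules) and restate power from step 2 of the working.
2. **Analyse serial X7 with a linear mixed model on all visits**, in place of visit-by-visit or paired tests, for Aims 1 and 3 and for RDS with versus without BPD: infant random effect, group, postnatal age at test, and group-by-age, limited to the age range that the groups share. Postnatal age is the better scale because the Aim 1 groups do not overlap in gestational age at birth, and because baseline follows enrolment, so visit number does not fix age.
3. **Aim 4.** Word all results as associations, including non-inferiority. Prespecify the pre/post interval. For treatments assessed over days or weeks, add as a supporting analysis the same model with a time-varying treatment term, taking the background trend from untreated infants with the same disease. State that the planned power (90%, or 80% for cromolyn) refers only to the one-group paired test, and reconcile 60 per arm with the paired design.

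**Cost.** More modelling on data already planned. No extra enrolment is needed if the initial value stays primary; a change score with ρ near 0.3 would need 184 per group for 90% power. Confounding by indication remains, early discharge of well infants is only partly handled, and the comparator-based Aim 4 estimate is less precise, at roughly 63% to 65% power with equal groups.
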